##### **5.1.2 Increase or Reduction in Dose of the Study Drug(s)**

During the study, subjects who experience a National Cancer Institute (NCI)-Common Terminology Criteria for Adverse Events (CTCAE) guidelines (version 4.03) grade 3 or higher AE (except liver function test [LFT] AE) toxicity that is attributed to the study drug and cannot be ameliorated by the use of adequate medical intervention and/or dose reduction may interrupt

- CONFIDENTIAL -

study drug treatment for 1 week or until the toxicity grade improves to grade 2 or lower in severity. Study drug may be restarted at the original dose (160 mg/day) or a reduced dose (120 mg or 80 mg/day). If restarted at a lower dose or if interrupted for > 2 weeks, the Medical Monitor must be consulted. After dose reduction, based on subject tolerance, study drug may be increased to a maximum dose of 160 mg/day per investigator discretion.

Enzalutamide must be interrupted during the evaluation of symptoms suspicious of PRES (headache, lethargy, confusion, blindness and other visual and neurological disturbances, with or without associated hypertension).

### **5.1.3 Previous and Concomitant Treatment (Medication and Nonmedication Therapy)**

Medications taken within 28 days prior to the screening visit and up to the first dose of study medication will be documented on the appropriate case report form (CRF) as a prior medication.

Medications taken after the first dose of study medication up until the final follow-up visit will be documented on the appropriate CRF as concomitant medication.

Prior and concomitant medications include all vitamins, herbal remedies, over the counter, and prescription medications.

#### **5.1.3.1 Required Concomitant Treatment**

All subjects are required to receive background therapy with ADT, either bilateral orchiectomy or an LHRH agonist or antagonist, which must be maintained during study treatment, as per standard of care (SOC).

An LHRH agonist or antagonist will be provided from the site's stock and administered in accordance with prescribing information.

#### **5.1.3.2 Prohibited Concomitant Treatment**

A list of excluded concomitant medications is provided in [\[Appendix 12.4 List of Excluded Concomitant Medications\]](#). The following medications are prohibited within 4 weeks of day 1 and during the study treatment period:

- 5  $\alpha$ -reductase inhibitors (finasteride, dutasteride);
- Estrogens;
- Cyproterone acetate, megestrol acetate;
- Biologic or other agents with antitumor activity against prostate cancer (with the exception of those therapies identified in exclusion criterion No. 1);
- Systemic glucocorticoids greater than the equivalent of 10 mg per day of prednisone intended for the treatment of prostate cancer;
- Herbal medications that have known hormonal antiprostate cancer activity and/or are known to decrease PSA levels (i.e., saw palmetto);

- CONFIDENTIAL -

- Androgens (testosterone, dihydroepiandrosterone, etc.);
- Investigational agents.

In addition, bisphosphonates and denosumab are prohibited unless stabilized for 2 weeks prior to randomization and held constant, as tolerated, throughout study treatment or administered for diagnosis of osteoporosis.

#### **5.1.3.3 Enzalutamide Drug Interaction**

There is a potential for enzalutamide to affect exposures to other medicinal products, or for other medicinal products to affect exposure to enzalutamide:

- Strong CYP2C8 inhibitors (e.g., gemfibrozil) are to be avoided. If subject must be coadministered a strong CYP2C8 inhibitor, the dose of enzalutamide should be reduced to 80 mg once daily. If coadministration of the strong inhibitor is discontinued, the enzalutamide dose should be returned to the dose used prior to initiation of the strong CYP2C8 inhibitor.
- Strong CYP3A4 inducers (e.g., carbamazepine, phenobarbital, phenytoin, rifampin) or moderate CYP3A4 inducers (e.g., bosentan, efavirenz, etravirine, modafinil, nafcillin, St. John's Wort) should be avoided if possible as they may reduce enzalutamide plasma concentration if coadministered. Selection of a concomitant medication with no or minimal CYP3A4 induction potential is recommended.
- Enzalutamide is a strong inducer of CYP3A4 and a moderate inducer of CYP2C9 and CYP2C19. Medicinal products with a narrow therapeutic range that are substrates of CYP3A4 (e.g., alfentanil, cyclosporine, dihydroergotamine, ergotamine, fentanyl, pimozide, quinidine, sirolimus, tacrolimus), CYP2C9 (e.g., phenytoin, warfarin), or CYP2C19, or UGT1A1 (e.g., S-mephenytoin) should be avoided if possible, as enzalutamide may decrease their exposure.
- If enzalutamide coadministration with warfarin cannot be avoided, additional international normalized ratio (INR) monitoring should be conducted.
- Enzalutamide is an inhibitor of human P-glycoprotein (P-gp) and may increase exposure to medicines that are P-gp substrates. Medicinal products with a narrow therapeutic range that are substrates for P-gp (e.g., digoxin, colchicine, dabigatran etexilate) should be used with caution when administered concomitantly with enzalutamide.

#### **5.1.3.4 Permitted Concomitant Treatment**

The following treatments are allowed during the study (and do not require study drug discontinuation) including, but not limited to:

- Blood transfusions and growth factor support per SOC and institutional guidelines;
- Steroid use (for indication other than prostate cancer) per SOC;
- Pain therapy per SOC and institutional guidelines;

- CONFIDENTIAL -

- Palliative radiation therapy including external beam radiotherapy or systemic radionuclides (e.g., Samarium or Strontium);
- Vaccine therapy that has prior market authorization and is not intended to treat prostate cancer;
- Palliative surgical procedures to treat skeletal-related events.

Hormonal treatment for treating complications of LHRH analogue treatment (e.g., hot flashes) will be allowed with Medical Monitor approval. In addition, flutamide, bicalutamide or nilutamide are permitted if given concurrently with LHRH agonist or antagonist to prevent flare (See [\[Appendix 12.9 Anti-Androgen Usage\]](#)).

#### **5.1.4 Treatment Compliance**

Study subjects should be counseled on the need to meet 100% compliance with study drug unless study drug is withheld for a toxicity. Investigator or designee should ensure that study subjects meet this goal throughout the study period. Compliance will be verified by the accounting of study drug. When study drug is administered at the research facility, it will be administered under the supervision of study personnel. If compliance per visit is less than 80% or higher than 120% of the planned dosage, and study drug was not withheld and there were no study drug reductions, the investigator or designee is to counsel the subject on the importance of taking the study drug.

Compliance of the study drug will be monitored by the accounting of unused medication returned by the subject at visits. Compliance will be documented.

#### **5.1.5 Criteria for Continuation of Treatment**

Not applicable.

#### **5.1.6 Restriction During the Study**

Not applicable.

### **5.2 Demographics and Baseline Characteristics**

#### **5.2.1 Demographics**

Demographic information will be collected at the screening visit for all subjects and will include age or date of birth, gender, race and ethnicity (as local regulations allow).

#### **5.2.2 Medical History**

Medical history will be collected at the screening visit for all subjects and includes all significant medical conditions that have occurred or are currently ongoing at time of consent. The condition, onset date and recovery date will be collected. NCI-CTCAE (version 4.03) grade will be collected for conditions that are ongoing at time of consent. Cancer risk factor information will also be collected.

- CONFIDENTIAL -

### **5.2.3 Diagnosis of the Target Disease, Severity, and Duration of Disease**

Prostate cancer history will be collected at the screening visit and will include histological or cytological diagnosis, date of diagnosis, Gleason score and associated treatment. Date of diagnosis of metastatic disease, location of metastatic disease lesions, and all previous and/or ongoing treatment will also be documented during screening visit.

## **5.3 Efficacy Assessment**

### **5.3.1 Efficacy Assessment**

#### **5.3.1.1 PSA**

Blood samples for PSA will be collected at each scheduled visit during study treatment and at the safety follow-up visit. All samples will be analyzed by sponsor designated central laboratory.

#### **5.3.1.2 CT/MRI and Bone Scan**

Radiographic imaging will be performed using CT or MRI and bone scan.

Radiographic assessments performed prior to informed consent, as part of routine care, may be used as the baseline assessment if performed within 6 weeks of day 1 and if digital format images are available for submission to the sponsor.

Following baseline imaging, subsequent scans including abdominal-pelvic CT, chest CT (if screening visit chest X-ray demonstrated metastatic chest disease) and bone scan will be repeated at day 85/week 13 visit and every 12 weeks thereafter. Imaging may be performed at any time to confirm suspected disease progression. Assessment will include tumor measurements for target lesions and nontarget lesions and assessment for any new lesions. An overall assessment will be documented for each time point evaluation. At the end of the study for each subject, an overall best response will be documented.

Study films should be read on site and also submitted in digital format to the sponsor designated facility in case independent central review is required after the end of study. The initial imaging/scanning technique should be applied for the duration of the study for the subject and assessed by the same site designated reader, whenever possible.

Radiographic disease progression is defined as progressive disease by RECIST version 1.1 for soft tissue disease or by appearance of 2 or more new lesions on bone scan. The documentation and confirmation required for the determination of radiographic progression is listed in [\[Table 2\]](#).

**Table 2 Protocol-specified Documentation for Radiographic Evidence of Disease Progression**

Date Progression Detected (Visit) †	Criteria for Progression	Criteria for Confirmation of Progression (Requirement and Timing)	Criteria for Documentation of Disease Progression on Confirmatory Scan
Week 13	Bone lesions: $\geq 2$ new lesions compared to baseline bone scan	Timing: $\geq 6$ weeks after progression identified or at week 25 visit	$\geq 2$ new bone lesions on bone scan compared to week 13 scan ( $\geq 4$ new lesions compared to baseline bone scan)
	Soft tissue lesions: progressive disease on CT or MRI by RECIST v1.1	No confirmatory scan required for soft tissue disease progression	Not applicable
Week 25 or Later	Bone lesions: $\geq 2$ new lesions on bone scan compared to best response on treatment	No confirmatory scan required	Not applicable
	Soft tissue lesions: progressive disease on CT or MRI by RECIST v1.1	No confirmatory scan required for soft tissue disease progression	Not applicable

CT: computed tomography; MRI: magnetic resonance imaging; RECIST v1.1: Response Evaluation Criteria in Solid Tumors version 1.1

† Progression detected by bone scan at an unscheduled visit prior to week 25 will require the same criteria for documentation of disease progression as week 13 with a confirmatory scan at least 6 weeks later or at the next scheduled scan.

Study drug treatment should be continued as long as the subject is tolerating the study drug and continues ADT until radiographic disease progression is documented as outlined in [Table 2] or the initiation of new antineoplastic therapy for treatment of prostate cancer. It is recommended that subjects remain on study treatment until radiographic disease progression is confirmed. Subjects who discontinue study treatment without confirmed radiographic progression will continue to be scanned every 12 weeks until radiographic progression is confirmed by investigator assessment or the required number of PSA progression events for the final analysis is reached.

### 5.3.1.3 Subject Reported Outcomes

Subject reported outcomes will be collected according to the schedule of assessments during onsite visits [Table 1].

#### BPI-SF

The BPI-SF pain questionnaire is a validated instrument that is a subject self-rating scale assessing level of pain, effect of the pain on activities of daily living and analgesic use. The BPI used in this study is the short form and contains 9 questions. The BPI uses simple numeric rating scales from 0 to 10.

### QLQ-PR25

The QLQ-PR25 is a 25-item module designed to assess QoL in prostate cancer subjects. The extent of occurrence of 25 defined symptoms related to bowel, bladder and hormones as well as interest in and occurrence of sexual activity are rated by selecting 1 of 4 categories ranging from not at all to very much.

### EQ-5D-5L

The EQ-5D-5L is a QoL instrument for self-reported assessment of 5 domains of health: mobility, self-care, usual activities, pain/discomfort and anxiety/depression. Each domain is rated by selecting 1 of 5 standardized categorizations ranging from no problem to extreme problem. The final question is a visual analogue scale to rank health status from best health imaginable to worst health imaginable.

### FACT-P

The FACT-P questionnaire is a multi-dimensional, self-reported QoL instrument specifically designed for use with prostate cancer subjects. It consists of 27 core items that assess subject function in 4 domains: physical, social/family, emotional, and functional wellbeing, which is further supplemented by 12 site-specific items to assess for prostate-related symptoms. Each item is rated on a 0 to 4 Likert-type scale.

## **5.4 Safety Assessment**

### **5.4.1 Vital Signs**

Routine vital signs, including blood pressure, pulse and temperature will be assessed at the screening visit, at every clinic visit while on study drug and at the safety follow-up visit.

### **5.4.2 Laboratory Assessments**

Routine laboratory samples for hematology, chemistry and PSA will be collected at the screening visit, at every clinic visit while on study drug and at the safety follow-up visit. Testosterone will be collected at week 13 and every subsequent 12 weeks while on study drug. Other laboratory assessments will be collected according to the schedule of assessments [Table 1]. PSA will be analyzed at sponsor designated central laboratory, other tests will be analyzed by each site itself. Analytes included are identified in [Table 3].

**Table 3 Laboratory Assessments**

Hematology	Biochemistry	Other
Red blood cell count	Albumin	Testosterone
White blood cell count	Alkaline phosphatase	PSA
White blood cell differential	Alanine aminotransferase	
Hemoglobin	Aspartate aminotransferase	
Hematocrit	Blood urea nitrogen	
Platelet count	Blood urea	
	Calcium	
	Creatinine	
	Glucose	
	Phosphorus	
	Potassium	
	Sodium	
	Total bilirubin	
	Total protein	

Clinical significance of out-of-range laboratory findings is to be determined and documented by the investigator/subinvestigator who is a qualified physician. Since a local or other clinical laboratory was used for hematology, biochemistry, testosterone and the urgent management of an AE, the reference ranges of the laboratory were provided to the sponsor or delegated CRO.

#### 5.4.3 Physical Examination

Complete physical examination will be performed at the screening visit to assess weight, height, general appearance, skin, eyes, ears, nose, throat, neck, cardiovascular, respiratory, gastrointestinal, musculoskeletal, neurologic status, mental status, lymphatic and genitourinary systems.

A brief physical examination with weight will be performed at day 1, all subsequent clinic visits while on study drug and at the safety follow-up visit. New or worsening clinically significant findings on physical examination will be recorded as AEs if they meet the criteria in [Section 5.5.1 Definition of Adverse Events].

#### 5.4.4 Electrocardiogram

Standard 12-lead ECGs will be performed at the local institution and interpreted by the local institution's medically trained staff. ECGs will be performed at screening, day 1 and the safety follow-up visit. Parameters that include heart rate, PR interval, RR interval, QRS interval, QT interval, and interpretation and clinical significance as judged by the investigator will be collected.

ECGs should be obtained after the subject has rested quietly and is awake in a fully supine position (or semirecumbent if supine is not tolerated) for 10 minutes. It is recommended that ECG reports are printed in duplicate and photocopied to prevent fading.

### 5.4.5 Imaging

See [[Section 5.3.1.2 CT/MRI and bone scan](#)] for detailed information regarding imaging.

### 5.4.6 Order of Assessments

Not applicable.

## 5.5 Adverse Events and Other Safety Aspects

### 5.5.1 Definition of Adverse Events

An AE is any untoward medical occurrence in a subject administered a study drug, and which does not necessarily have to have a causal relationship with this treatment. An AE can therefore be any unfavorable and unintended sign (including an abnormal laboratory finding), symptom, or disease (new or exacerbated) temporally associated with the use of a medicinal product whether or not considered related to the medicinal product.

In order to identify any events that may be associated with study procedures and could lead to a change in the conduct of the study, Astellas collects AEs even if the subject has not received study drug treatment. AE collection begins after the signing of the informed consent for the double-blind period and will be collected until 30 days after the last dose of study drug (including the double-blind period and open-label phase if applicable), or initiation of a new therapy for prostate cancer, or the subject is determined to be a screen failure, whichever occurs first. During the post treatment follow-up period, only symptomatic skeletal events need to be reported.

Care will be taken not to introduce bias when detecting AEs and/or SAEs. Open-ended and non-leading verbal questioning of the subject is the preferred method to inquire about AE occurrences.

Some sites may have additional local requirements for events that are required to be reported as AEs or in an expedited manner similar to a SAE. In these cases, it is the investigator's responsibility to ensure these AEs or other reporting requirements are followed and the information is appropriately recorded in the electronic case report form (eCRF) accordingly.

An abnormality identified during a medical test (e.g., laboratory parameter, vital sign, ECG data, physical examination) should be defined as an AE only if the abnormality meets 1 of the following criteria:

- Induces clinical signs or symptoms;
- Requires active intervention;
- Requires interruption or discontinuation of study medication;
- The abnormality or investigational value is clinically significant in the opinion of the investigator.

- CONFIDENTIAL -

### **5.5.1.1 Abnormal Laboratory Findings**

Any abnormal laboratory test result (e.g. hematology, clinical chemistry, or urinalysis) or other safety assessment (e.g., ECGs, radiographic scans, vital signs measurements, physical examination), including those that worsen from baseline, that is considered to be clinically significant in the medical and scientific judgment of the investigator and not related to underlying disease, is to be reported as an (S)AE.

Any clinically significant abnormal laboratory finding or other abnormal safety assessment which is associated with the underlying disease does not require reporting as an (S)AE, unless judged by the investigator to be more severe than expected for the subject's condition.

Repeating an abnormal laboratory test or other safety assessment, in the absence of any of the above criteria, does not constitute an AE. Any abnormal test result that is determined to be an error does not require reporting as an AE.

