### **5.5.1.2 Potential Cases of Drug-Induced Liver Injury**

Refer to [\[Appendix 12.5 Liver Safety Monitoring and Assessment\]](#) for detailed instructions on Drug Induced Liver Injury (DILI). Abnormal values in aspartate transaminase (AST) and/or alanine transaminase (ALT) concurrent or with abnormal elevations in total bilirubin that meet the criteria outlined in [\[Appendix 12.5 Liver Safety Monitoring and Assessment\]](#), in the absence of other causes of liver injury, are considered potential cases of drug-induced liver injury (potential Hy's Law cases) and are always to be considered important medical events and reported per [\[Section 5.5.5 Reporting of Serious Adverse Events\]](#).

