### **7.5.2 Laboratory Assessments**

Clinical laboratory evaluations (including hematology and serum chemistry) will be presented for each visit using descriptive statistics (n, mean, SD, median, minimum and maximum values). Change from baseline will also be presented. Shift analysis tables will present the shift from baseline for using NCI-CTCAE grade and lab reference range indicator. All clinically significant abnormal laboratory values will be recorded as AEs and graded using NCI-CTCAE guidelines. A listing of subject laboratory values will be provided.

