### **12.6 Common Serious Adverse Events**

The following is a list of SAEs that the sponsor considers to be associated with the disease state being studied. The list does **NOT** change the investigator’s reporting obligations or prevent the need to report an AE meeting the definition of an SAE as detailed in [[Section 5.5.2 Definition of Serious Adverse Events](#)]. The purpose of this list is to note that some events reported as SAEs may not require expedited reporting to the regulatory authorities based on the classification of “common SAEs.” The investigator is required to follow the requirements detailed in [[Section 5.5.5 Reporting of Serious Adverse Events](#)].

For IND safety reporting, single occurrences of the following events may be excluded from expedited reporting to the cFDA. If aggregate analysis of these events indicates they occur more frequently with study drug, an expedited IND safety report may be submitted to the cFDA.

- Anemia
- Anorexia
- Asthenia/Fatigue
- Bone pain
- Back pain
- Catheter-related infection
- Dyspnea
- Hematuria
- Hydronephrosis
- Metastases to bone
- Metastases to central nervous system
- Nausea
- Obstructive uropathy
- Pain

- CONFIDENTIAL -

- Prostate cancer metastatic
- Renal failure
- Renal failure acute
- Spinal compression fracture
- Spinal cord compression
- Urinary retention
- Urinary tract infection
- Urinary tract obstruction
- Vomiting

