Neutrophil count decreased	Preferred terms of 'Neutrophil count decreased', 'Neutropenia', 'Agranulocytosis', 'Granulocyte count decreased', 'Granulocytopenia', 'Febrile neutropenia', 'Neutrophil percentage decreased', 'Band neutrophil count decreased', 'Band neutrophil percentage decreased', 'Neutropenic sepsis', 'Neutropenic infection' and 'Neutrophil count abnormal'
Cognitive/memory impairment	All preferred terms under the MedDRA High Level Group Term: 'Mental impairment disorders'
Ischemic Heart Disease	Narrow SMQs of 'Myocardial Infarction' and 'Other Ischaemic Heart Disease'
Other selected cardiovascular events	Narrow SMQs of 'Haemorrhagic central nervous system vascular conditions', 'Ischaemic central nervous system vascular conditions' and 'Cardiac failure'
Posterior reversible encephalopathy syndrome	Preferred term 'Posterior reversible encephalopathy syndrome'
Fatigue	Preferred terms of 'Fatigue', 'Asthenia'
Fall	Preferred term 'Fall'
Fractures	All preferred terms under the MedDRA High Level Group Terms: 'Fractures' and 'Bone and joint injuries'
Loss of consciousness	Preferred terms of 'Loss of consciousness', 'Syncope', 'Presyncope'
Thrombocytopenia	Preferred terms of 'Thrombocytopenia', 'Platelet count decreased'
Musculoskeletal events	Preferred terms of 'Back pain', 'Arthralgia', 'Myalgia', 'Musculoskeletal pain', 'Pain in extremity', 'Musculoskeletal stiffness', 'Muscular weakness', 'Muscle spasms'
Severe cutaneous adverse reactions (SCAR)	Narrow SMQ of 'Severe cutaneous adverse reactions'
Angioedema	Narrow SMQ of 'Angioedema'
Rash	All preferred terms including term 'Rash'

Event of special interest	Selection based on MedDRA 23.0

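### Protocol 5.5.1.1 and 7.5.2 give incompatible rules for recording disease-associated laboratory abnormalities as AEs, and the SAP's attribution-free grade-shift tables cover enzalutamide only

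*Protocol*

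**What the plan says.** Four protocol sections bear on when an abnormal laboratory value becomes an AE.

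- **Protocol 5.5.1** lists four criteria and allows a test abnormality to count as an AE only if it meets one of them. One criterion is: "The abnormality or investigational value is clinically significant in the opinion of the investigator".
- **Protocol 5.5.1.1**, a subsection of 5.5.1, gives the reporting rule. A result that is "clinically significant in the medical and scientific judgment of the investigator and not related to underlying disease, is to be reported as an (S)AE". A clinically significant finding "which is associated with the underlying disease does not require reporting as an (S)AE". That exemption has one limit, since it holds only "unless judged by the investigator to be more severe than expected for the subject's condition".
- **Protocol 5.5.1.3** leaves events that clearly fit expected progression out of the AE record. It sends doubtful cases, and those where evidence points to study drug, to (S)AE reporting.
- **Protocol 7.5.2** says: "All clinically significant abnormal laboratory values will be recorded as AEs and graded using NCI-CTCAE guidelines". It makes no exception for the underlying disease.

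On the analysis side, Table 7 in SAP 6.2 selects the thrombocytopenia event of special interest by "Preferred terms of 'Thrombocytopenia', 'Platelet count decreased", and the neutrophil event from a longer list of AE terms. SAP 7.5.1 builds the grade 3 or higher tables from reported treatment-emergent AEs.

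SAP 7.5.2 separately summarises laboratory values and their CTCAE grades by visit. It specifies the grade-shift tables, including the shift to the highest post-baseline grade, for the enzalutamide group only. Protocol 7.5.2 plans shift tables without that restriction.

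**The concern.** In metastatic prostate cancer, anaemia and low counts can readily be put down to the cancer. Anaemia is in the Appendix 12.6 list, which opens: "The following is a list of SAEs that the sponsor considers to be associated with the disease state being studied". That list does not change reporting duties, but it shows that disease attribution is foreseeable.

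A low count that the investigator regards as expected disease is an AE under Protocol 7.5.2 and need not be one under 5.5.1.1. A reader who relies on 7.5.2 will take the AE tables to hold every clinically significant value. If sites worked to 5.5.1.1, the tables hold fewer. Neutropenia is one of the events of special interest that Protocol 1.3 names for enzalutamide, so the content of these tables matters.

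The second issue is comparability. Attribution may follow the visible course of disease, and the design expects that course to differ by arm: the sample-size section assumes a median time to PSA progression of about 18 months on enzalutamide and 9 on placebo.

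**Working it through.** The plan states no figure on this point, so there is none to reproduce. The check compares the rules case by case and then sizes the effect on assumed values.

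**Step 1: where the rules differ.** For a clinically significant laboratory value:

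| Investigator's view | 5.5.1.1 with 5.5.1.3 | 7.5.2 |
|---|---|---|
| Not related to the cancer | report | record |
| Disease-associated, worse than expected | report | record |
| Possible progression event, but doubtful or drug suspected | report | record |
| Disease-associated, as expected | not required | record |

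Only the last row conflicts. Nothing in the protocol or SAP says which rule prevails.

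**Step 2: which outputs inherit the conflict.** Outputs built from AE terms do: the two cytopenia events of special interest and the general and grade 3 or higher AE tables. Anaemia is not in SAP Table 7, so it is affected only through the general and graded tables. Outputs built from laboratory values do not inherit it: the visit summaries and graded summaries in SAP 7.5.2, and the liver thresholds by treatment group in SAP 7.5.2.1.

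**Step 3: size.** Let p be the true rate of clinically significant abnormality and f the share attributed to the cancer and not reported. The AE rate is p under 7.5.2 and p(1 − f) under 5.5.1.1. With the same p in both arms, the false gap (enzalutamide minus placebo) is p × (f placebo − f enzalutamide). All values of p and f below are assumptions.

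| p, both arms | f enzalutamide | f placebo | Shown, enzalutamide | Shown, placebo | Gap |
|---|---|---|---|---|---|
| 15% | 30% | 30% | 0.15 × 0.70 = 10.5% | 0.15 × 0.70 = 10.5% | 0 |
| 10% | 20% | 50% | 0.10 × 0.80 = 8% | 0.10 × 0.50 = 5% | 3 points |
| 20% | 20% | 40% | 0.20 × 0.80 = 16% | 0.20 × 0.60 = 12% | 4 points |
| 15% | 30% | 60% | 0.15 × 0.70 = 10.5% | 0.15 × 0.40 = 6.0% | 4.5 points |

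Over p of 10% to 30% and attribution differences of 10 to 30 points, the gap runs from 0.10 × 0.10 = 1 point to 0.30 × 0.30 = 9 points. It reverses sign if attribution is more frequent on enzalutamide. With equal f there is no false gap, but both rates are multiplied by (1 − f), and so is any true difference between arms.

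**Step 4: scale.** With 120 and 60 patients, the standard error of the 16% versus 12% difference is √(0.16 × 0.84/120 + 0.12 × 0.88/60) = √(0.00112 + 0.00176) = 5.4 points. A false gap of 4 points is therefore smaller than one standard error of the comparison.

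**The case against.** The case on the other side has several parts.

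- **5.5.1 need not conflict with 5.5.1.1.** Its criteria are worded as a necessary condition, and 5.5.1.1 then narrows them for laboratory findings. This stands. A reader might infer a three-way contradiction, but the firm conflict is between 5.5.1.1 and 7.5.2.
- **7.5.2 is an analysis section.** Sites would normally take reporting instructions from 5.5, so mixed practice between sites is conjecture. This stands too, but it does not rescue 7.5.2. If every site follows 5.5.1.1, the statement in 7.5.2 is untrue of the resulting tables.
- **The exemption is limited.** Reporting is not required, rather than forbidden. Findings worse than expected come back in, and 5.5.1.3 returns doubtful and drug-suspected progression events. This narrows the gap to the last row of Step 1 without closing it.
- **Liver is largely protected.** Under 5.5.1.2, transaminase and bilirubin elevations meeting the Appendix 12.5 criteria, "in the absence of other causes of liver injury, are considered potential cases of drug-induced liver injury" and must be reported. SAP 7.5.2.1 also tabulates thresholds by arm from laboratory values. Only liver findings given another cause, such as the cancer, remain exposed in the AE tables.
- **Attribution is made blind, and often before radiographic progression.** Study drug normally stops at radiographic progression, and AE collection ends 30 days after the last dose or at new therapy. This weakens the route to bias between arms. It does not remove it, because treatment normally continues through PSA progression, which is expected earlier on placebo.
- **Laboratory summaries are free of attribution.** This is correct, and it is the main mitigation. It is incomplete because the SAP limits the shift and worst-grade tables to enzalutamide.

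**Conclusion.** The inconsistency is real and needs no assumption: 5.5.1.1 and 7.5.2 cannot both describe the AE data. It reaches only the AE-term tables. The primary endpoint is untouched.

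A reader might infer that the AE tables will show a false excess of cytopenia or anaemia on enzalutamide. The documents do not support that. They give no attribution rates, investigators are blinded, and the gap of 1 to 9 points rests wholly on assumed rates and an assumed difference in attribution. With equal attribution the tables are only understated. A reader might also infer that liver rates are seriously affected, but 5.5.1.2 and the by-arm liver table largely prevent it.

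The AE tables should nevertheless not be read as complete for clinically significant laboratory abnormalities until one rule is stated. The worst-grade comparison that would settle doubts about attribution is not specified for placebo in the SAP.

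**What to change.** 1. **State one rule in Protocol 5.5.1.1 and 7.5.2, consistent with 5.5.1.3.** There are two ways to do this:
   - Record every clinically significant laboratory value as an AE, with a flag for disease-associated ones, and show the flagged events separately by arm. Section 5.5.1.3 must then say how such values are kept apart from progression events that are not recorded as AEs. The cost is an eCRF flag and a few more AE records. At this stage (protocol version 5.0, SAP 1.0 of 21 December 2022) it would also split the AE data into periods before and after the change unless earlier records were reworked.
   - If collection can no longer change, correct 7.5.2 to say that disease-associated findings are exempt under 5.5.1.1 and may be absent from the AE tables. The cost is wording only.
2. **In either case, produce the CTCAE shift and worst-grade laboratory tables in SAP 7.5.2 for both arms.** Cytopenia and anaemia can then be compared without attribution. This uses data already collected, restores what Protocol 7.5.2 plans, and costs one extra set of columns in existing tables.
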